### **Dexamethasone Toxicity**

For management of dexamethasone toxicity, see Table 11.

**Table 11.** If dexamethasone is permanently discontinued due to toxicity, pre- and post-infusion doses administered on the day of isatuximab dosing may be given at the investigator's discretion.

Table 11 represents suggested dose modifications of dexamethasone, but physician discretion and clinical judgment should prevail.

The maximum delay for toxicity before treatment is permanently discontinued will be 3 weeks; however, delays due to other circumstances should be discussed with the Principal Investigator.

Delays of >3 weeks must be discussed with the Principal Investigator. Re-treatment will be at the discretion of the Principal Investigator.

### **Treatment Discontinuation**

Administration of isatuximab, carfilzomib, lenalidomide and dexamethasone can be discontinued permanently in the event of a treatment-related toxicity at the Treating Investigator's discretion.

If a delay of starting a new cycle is greater than 21 days, the subject should be discontinued from treatment, unless continuing treatment is mutually agreed upon by the Treating Investigator and the Lead Principal Investigator.

If isatuximab, carfilzomib, or lenalidomide requires permanent discontinuation before Cycle 4 induction, the subject's treatment will be discontinued at the end of Cycle 4 induction. If isatuximab, carfilzomib or lenalidomide requires permanent discontinuation during maintenance cycles, the subject may remain on study with the remaining drug(s). Dexamethasone may be discontinued without the subject discontinuing study treatment.

## **7. ADVERSE EVENTS: LIST AND REPORTING REQUIREMENTS**

Adverse event (AE) monitoring and reporting is a routine part of every clinical trial. Pretreatment symptoms/conditions to be graded at baseline and AEs to be graded at each evaluation per NCI-CTCAE v 5.0 grading.

### Adverse Event List for Investigational Agent, Isatuximab:

#### **Possible risks**

Beside hematological malignancies, the CD38 antigen is expressed on normal immune cells and despite the lack of significant depletion in the in vitro studies, isatuximab could modulate cell survival and differentiation of both lymphoid and myeloid cells in cancer patients. This modulation could increase the risk for infections. In addition, while no association between transient cytokine increases and the occurrence of IRs has been demonstrated in patients, administration of isatuximab in the clinical setting has been correlated with a single occurrence of nonserious Grade 2 cytokine release syndrome at Cycle 1, reported as a medical diagnosis in a patient who subsequently received further administrations of single agent isatuximab without recurrence of symptoms suggestive of cytokine release syndrome.

The CD38 antigen is also expressed in several normal nonlymphoid human tissues:

- Strong specific staining was observed in the glandular epithelial cells of prostate tissues.
- Moderate to strong specific staining was observed in the endothelial cells lining the pituitary gland.
- Moderate focal staining of round cells compatible with Kupffer cells was observed in the liver.
- Staining of astrocytes in the brain and bronchial epithelium cells in the lungs was observed in a non-GLP study, though this finding was not observed in the definitive GLP tissue cross-reactivity study.

Evaluation of prostate specific antigen and pituitary hormone values were systematically assessed before each isatuximab treatment cycle in the first-in-human Phase 1 single agent trial TED10893.

Among the 89 patients treated in Study TED10893 Phase 1, the reported laboratory abnormalities and AE do not suggest an effect of the study treatment on these organ functions. Therefore, those systematic laboratory assessments during study treatment have no longer been considered necessary in the subsequent clinical studies.

Close monitoring of safety is required during the clinical studies and clinical exams are systematically recorded in the case report forms. Beside any tests to be performed when clinically indicated, parameters analyzed routinely until the end of treatment visit in the study protocols include: physical examination, vital signs, all AEs/Serious AEs (SAE), echocardiogram (ECG), and laboratory findings. These analyses required in all the patients during the clinical studies provide an adequate method to detect specific organ function abnormalities.

### **Possible adverse drug reactions**

Within the context of IARs, anaphylactic reaction, cytokine release syndrome, and pyrexia are among the adverse reactions observed in patients treated with isatuximab; these reactions may involve immunogenicity mechanisms (human antihuman antigen) and hypersensitivity reactions, and are well-known to occur in association with other therapeutic mAb proteins. These adverse reactions, whether acute or delayed, may be serious and systemic.

### **Drug interactions**

No drug-drug interaction has been observed between isatuximab other drugs used in combination (lenalidomide, pomalidomide).

### **Contraindications**

Contraindications include:

- Known intolerance or hypersensitivity to infused proteins products, sucrose, histidine, and polysorbate 80.
- Pregnant or lactating women.

**Adverse Event List(s) for Commercial Agent(s): carfilzomib, lenalidomide, dexamethasone**

For each commercial agent, please refer to the package insert(s) for the comprehensive list of adverse events.

**Adverse Events**

**7.1 Definitions**

**Adverse Event (AE)**

An AE is any undesirable sign, symptom or medical condition or experience that develops or worsens in severity after starting the first dose of study treatment or any procedure specified in the protocol, even if the event is not considered to be related to the study.

An adverse event is any change in health occurring in a person who is a participant in biomedical research, whether this change is related or not to the research or to the product that the research is being conducted on. This includes any newly occurring event or previous condition that has increased in severity or frequency since the administration of drug.

For this protocol, an abnormal laboratory value will not be assessed as an AE unless that value leads to discontinuation or delay in treatment, dose modification, therapeutic intervention, or is considered by the investigator to be a clinically significant change from baseline.

**Serious adverse event (SAE) and events requiring expedited reporting**

A serious adverse event is an undesirable sign, symptom, or medical condition, regardless of causality that:

- Results in death;
- Is life-threatening. Life-threatening means that the participant was at immediate risk of death from the reaction as it occurred, i.e., it does not include a reaction which hypothetically might have caused death had it occurred in a more severe form;
- Requires hospitalization or prolongation of existing hospitalization (i.e., the event required at least a 24-hour hospitalization or prolonged a hospitalization beyond the expected length of stay). Hospitalization admissions and/or surgical operations scheduled to occur during the study period, but planned prior to study entry are not considered SAEs if the illness or disease existed before the participant was enrolled in the trial, provided that it did not

deteriorate in an unexpected manner during the trial (e.g., surgery performed earlier than planned);

- Results in persistent or significant disability/incapacity. Disability is defined as a substantial disruption of a person's ability to conduct normal life functions;
- Is a congenital abnormality or birth defect;
- Is an important medical event. An important medical event is an event that, when based upon appropriate medical judgment may jeopardize the participant and require medical or surgical intervention to prevent one of the outcomes listed above. Examples of such medical events include allergic bronchospasm requiring intensive treatment in an emergency room or at home, blood dyscrasias or convulsions that do not result in inpatient hospitalization, the development of drug dependency or drug abuse, or suspected transmission of infectious agents by medicinal product.

The following event must also be reported in an expedited manner:

- Results in pregnancy.
- Any adverse event arising after study treatment discontinuation/study termination that is possibly related to study treatments/procedures must be reported regardless of the delay between event onset and study treatment discontinuation/study termination.
- Secondary malignancies must be reported as serious adverse events regardless of when they occur and regardless of their relationship to the study treatments/procedures.

Events **not** considered to be serious adverse events are hospitalizations for:

- Routine treatment or monitoring of the studied indication, not associated with any deterioration in condition, or for elective procedures of a condition unrelated to the studied indication or its treatment.
- Elective or pre-planned treatment for a pre-existing condition that did not worsen.
- Emergency outpatient treatment for an event not fulfilling the serious criteria outlined above and not resulting in inpatient admission.
- Respite care.

**Please note the distinction between seriousness and severity of an AE.** Severity is a measure of intensity of an event (mild, moderate, severe). However, the event itself may be of relatively minor medical significance; thus, a severe reaction may not necessarily be classified as a serious reaction. This differs from seriousness, which is based on patient/event outcome or action criteria described above and are usually associated with events that pose a threat to a patient's life or functioning. A severe adverse event does not necessarily need to be considered serious. **Seriousness (not severity) serves as a guide for defining regulatory reporting obligations.**

Adverse Events of Special Interest

Adverse events of special interest (AESIs): An AE of special interest (serious or non-serious) is one of scientific and medical concern specific to the sponsor's product or program, for which

ongoing monitoring and rapid communication by the investigator to the sponsor can be appropriate. Such an event might warrant further investigation in order to characterize and understand it. Depending on the nature of the event, rapid communication by the trial sponsor to other parties (eg, regulators) might also be warranted. The AEs for this study are:

- Infusion reactions:  $\geq$ Grade 3
- Infections:  $\geq$ Grade 4
- Cytopenias:  $\geq$ Grade 4
- Tumor Lysis Syndrome (if present, qualifies as Grade 3 or higher per CTCAE V5.0 guidelines)
- Intervascular Hemolysis – all grades
- New primary malignancies (if present, qualifies as Grade 3 or higher per CTCAE V 5.0 guidelines), regardless of causal relationship to study drug(s), occurring at any time for the duration of the study, from the time of signing informed consent for at least 3 years, after the last dose of investigational product.

Adverse Events of Special Interest are only reported by sites in an expedited manner if the event meets the criteria for an SAE (as per Section). All other AESIs will be collected in the SDC, but do not require immediate submission.

### **Pregnancy**

Pregnancies and suspected pregnancies (including a positive pregnancy test regardless of age or disease state) of a female participant occurring while the participant is on study drug or within 28 days of the participant's last dose of study drug are to be reported immediately to Massachusetts General Hospital. If the participant is on study drug, the study drug is to be discontinued immediately and the participant is to be instructed to return any unused portion of the study drug to the Investigator. The pregnancy, suspected pregnancy, or positive pregnancy test must be reported immediately of the investigator's knowledge of the pregnancy by phone and e-mail/facsimile to the lead site using the Pregnancy Reporting Form. Immediately upon receipt of this report, the lead site will inform study pharmaceutical partners using the Pregnancy Reporting Form.

The female should be referred to an obstetrician/gynecologist experienced in reproductive toxicity for further evaluation and counseling.

The investigator will follow the female participant until completion of the pregnancy and must notify the lead site of the outcome of the pregnancy (including notification of false-positive tests) within 24 hours of having knowledge of the event by email/facsimile using the Follow-Up Pregnancy Reporting Form.

If the outcome of the pregnancy meets the criteria for immediate classification as a SAE (i.e.,

spontaneous abortion [any congenital anomaly detected in an aborted fetus is to be documented], stillbirth, neonatal death, or congenital anomaly [including that in an aborted fetus]), the investigator should follow the procedures for reporting SAEs (i.e., report the event to the lead site, within 24 hours of the investigator's knowledge of the event by e-mail or facsimile).

All neonatal deaths that occur within 28 days of birth should be reported, without regard to causality, as SAEs. In addition, any infant death after 28 days that the investigator suspects is related to the *in utero* exposure to the study drug should also be reported to the lead site, within 24 hours of the investigator's knowledge of the event by e-mail or facsimile.

In the case of a live "normal" birth, the lead site should be advised as soon as the information is available.

If the female is found not to be pregnant, any determination regarding the participant's continued participation in the study will be determined by the investigator.

Female partners of a male taking investigational product should be advised to call their healthcare provider immediately if they get pregnant. The male participant should notify the investigator of his partner's pregnancy and her healthcare provider information. The investigator will then provide this information to the lead site for follow-up as necessary.

The pharmaceutical partner may in accordance with local data privacy laws request the subject's physicians' contact information in order to follow-up the pregnancy until birth outcome. The lead site shall provide the pharmaceutical company with all reasonably requested information (within the timeframe requested by company) to enable company to evaluate and submit complete single case and aggregate safety reports to regulatory agencies according to regulatory reporting requirements, and otherwise comply with applicable law.

### **Expectedness**

Adverse events can be "Expected" or "Unexpected."

### **Expected adverse event**

Expected adverse events are those that have been previously identified as resulting from administration of the agent. For the purposes of this study, an adverse event is considered **expected** when it appears in the current Investigator's Brochure or is included in the informed consent document as a potential risk. Scheduled hospitalizations for the study treatment, participant follow-up and medical conditions related to the progression of the disease are considered to be expected SAEs.

The investigator must evaluate all abnormal lab results to determine the clinical significance. If an abnormal result appears to be clinically significant, it must be considered to be an AE.

## Unexpected adverse event

For the purposes of this study, an adverse event is considered **unexpected** when it varies in nature, intensity or frequency from information provided in the current Investigator’s Brochure, section 6 of the protocol, or when it is not included in the informed consent document as a potential risk.

### Attribution (Causality)

Attribution is the relationship between an adverse event or serious adverse event and the study treatment. It will be assigned by using the WHO causality method assessment linked to CTCAE grading system (as follows):

Term	Description
Certain/Definite	A clinical event, including laboratory test abnormality, occurring in a plausible time relationship to drug administration, and which cannot be explained by concurrent disease or other drugs or chemicals. The response to withdrawal of the drug (de-challenge) should be clinically plausible. The event must be definitive pharmacologically or phenomenologically, using a satisfactory re-challenge procedure if necessary. The AE is clearly related to the study treatment.
Likely/Probable	A clinical event, including laboratory test abnormality, with a reasonable time sequence to administration of the drug, unlikely to be attributed to concurrent disease or other drugs or chemicals, and which follows a clinically reasonable response on withdrawal (de-challenge). Re-challenge information is not required to fulfill this definition. The AE is likely related to the study treatment.
Possible	A clinical event, including laboratory test abnormality, with a reasonable time sequence to administration of the drug, but which could also be explained by concurrent disease or other drugs or chemicals. Information on drug withdrawal may be lacking or unclear. The AE may be related to the study treatment.
Unlikely	A clinical event, including laboratory test abnormality, with a temporal relationship to drug administration which makes a causal relationship improbable, and in which other drugs, chemicals or underlying disease provide plausible explanations. The AE is doubtfully related to the study treatment.
Unrelated	The AE is clearly NOT related to the study treatment.

An event will be considered possibly study-related if causality criteria will be “certain/definite,” “likely/probable,” and “possible.”

The causality criteria “unlikely” and “unrelated” is intended to be used when the exclusion of drug causality of a clinical event seems most plausible. It will be used to define “not study-related” events.

An event will also be considered as “concomitant drug-related,” “disease progression-related” or “other cause related.”

Causality will be assessed for each investigational treatment used in the trial (bortezomib, lenalidomide and dexamethasone).

If a reported SAE is considered an unexpected and suspected serious adverse reaction (SUSAR), reporting/notification rules described below must be followed.

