## **1. OBJECTIVES**

### **1.1 Study Design**

A phase II study to evaluate the efficacy of once weekly carfilzomib, lenalidomide, dexamethasone, and isatuximab (KRDI) in patients with newly diagnosed, transplant-eligible multiple myeloma.

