### **5. TREATMENT PLAN**

#### **5.1 Treatment Regimen**

Carfilzomib, lenalidomide, dexamethasone, and isatuximab will be administered on a 28-day treatment cycle. All subjects will perform stem cell collection after 4 cycles of therapy.

For patient undergoing upfront stem cell transplant (SCT):

4 cycles of therapy followed by stem cell collection, high-dose chemotherapy, and autologous SCT followed by 2 additional cycles of therapy then maintenance.

For patients deferring SCT following collection:

4 cycles of therapy followed by stem cell collection followed by 4 additional cycles of therapy then maintenance.

Carfilzomib 56 mg/m^2 IV on Days 1, 8, 15

Lenalidomide 25 mg orally (po) on Days 1-21

Isatuximab 10 mg/kg IV Q1 week for 8 weeks, then Q2 weeks for 16 weeks, thereafter Q4 weeks

Dexamethasone 20 mg po will be administered day of and day after all doses of carfilzomib (Days 1, 2, 8, 9, 15, and 16) and isatuximab (Cycles 1 and 2 Days 22 and 23). The dexamethasone 20 mg oral or IV dose administered as a preinfusion medication on isatuximab infusion days (Days 1, 8, 15, 22) replaces the oral dexamethasone dose for that day.

\*All subjects with receive carfilzomib 20 mg/m^2 on Day 1 Cycle 1

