**Maintenance:**

Patients must achieve a PR or better to continue onto maintenance therapy on the study.

28-day Maintenance Cycle until progressive disease (PD) or unacceptable toxicity. Subjects will be stratified based on cytogenetics (deletion (del) 17, translocation (t)(4:14), t(14;16), t(14;20), 1q duplication).

Standard-risk:

Lenalidomide 10 mg po Days 1-21

High-risk:

Carfilzomib 56 mg/m^2 (or last tolerated dose) IV Days 1, 15

Lenalidomide 10 mg po Days 1-21

Isatuximab 10 mg/kg IV Day 1 for up to 24 cycles of maintenance (two years), then discontinue

In the maintenance phase, dexamethasone, 20 mg orally or IV will be administered to subjects as a preinfusion medication prior to isatuximab dosing. When dexamethasone is reduced to 20 mg/week and is given as preinfusion medication, subjects may receive low-dose methylprednisolone ( $\leq 20$  mg) orally (or equivalent in accordance with local standards) for the prevention of delayed infusion-associated reactions (IARs), as clinically indicated.

Because lenalidomide is primarily excreted unchanged by the kidney, adjustments to the starting dose of lenalidomide are recommended to provide appropriate drug exposure in patients with renal impairment. Lenalidomide dose adjustment should be instituted for patients with a CrCl  $\leq 50$  mL/min. The recommended doses for patients with multiple myeloma and renal impairment are shown below in Table 9. If during treatment a patient's renal status changes, the dose should be adjusted as shown in Table 9. Similarly, adjustments to the starting and ongoing dosing of carfilzomib are recommended in the setting of hepatic impairment. The doses should be adjusted as shown in Table 10.

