## 5.2 Pre-Treatment Criteria

A new cycle of treatment may begin on the scheduled Day 1 of a new cycle if the following criteria are met within 24 hours of Day 1:

- ANC  $\geq 1,000/\text{mm}^3$  (growth factor support is permitted during cycles with the exception of Cycle 1 Day 1 (C1D1); it is allowed on the same day as treatment administration).
- Platelet count  $\geq 50,000/\text{mm}^3$  (platelet support is permitted during cycles of treatment; it is allowed on the same day as treatment administration, including C1D1).
- Any lenalidomide-related allergic reaction/hypersensitivity or sinus bradycardia/other cardiac arrhythmia AE that may have occurred has resolved to < Grade 1.
- Any other lenalidomide, carfilzomib, or isatuximab-related adverse event that may have occurred has resolved to <Grade 2.
- Herpes zoster lesions, if present, are dry.

If these conditions are not met on Day 1 of a new cycle, the subject will be evaluated weekly and a new cycle of therapy will not be initiated until the toxicity has resolved as described above. The maximum amount of time that treatment may be held for these toxicities to resolve is 3 weeks. If drug is held for more than 3 weeks due to toxicity, the patient is to discontinue all study treatment and enter the survival follow-up phase of the study.

For intra-cycle dosing on days where laboratory studies are scheduled, the following criteria must be met:

- Platelet count  $\geq 30,000$  (platelet transfusion support is permitted to meet criteria)
- Absolute neutrophil  $\geq 500/\text{mm}^3$  (growth factor support is permitted during cycles with the exception of Cycle 1 Day 1 (C1D1); it is allowed on the same day as treatment administration).

Intra-cycle dose modifications for all drugs will be allowed based on toxicity and according to dose modifications outline in Section 6.1, Table 9.

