#### **5.3.1.10 Availability and Ordering**

Sanofi will supply isatuximab free-of-charge, shipped directly to the pharmacy at the study site. The investigator or designee will order isatuximab from Sanofi according to the ordering instructions provided by the company.

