### **5.3.2.9 Availability and Ordering**

Amgen will supply carfilzomib free-of-charge, shipped directly to the pharmacy at the study site. The investigator or designee will order carfilzomib from Amgen according to the ordering instructions provided by the company.

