### Dose Delay and Toxicity Management

ONLY if any of the following criteria are met and the event cannot be ascribed to lenalidomide, carfilzomib, dexamethasone, or underlying MM, the isatuximab infusion must be held to allow for recovery from toxicity. The criteria for a dose delay are:

- Grade 4 hematologic toxicity (except for Grade 4 lymphopenia), or Grade 3 or higher thrombocytopenia with bleeding.
- Febrile neutropenia of any grade.
- Neutropenia with infection, of any grade.
- Grade 3 or higher nonhematologic toxicities with the following exceptions:
  - Grade 3 nausea or Grade 3 vomiting that responds to antiemetic treatment.
  - Grade 3 diarrhea that responds to antidiarrheal treatment.
  - Grade 3 fatigue or asthenia that was present at baseline and lasts for <7 days after the last administration of isatuximab.
  - Grade 3 or 4 electrolyte disturbances which can be managed with replacement therapy.

If isatuximab administration does not commence within the prespecified window (Table 8) of the scheduled administration date, then the dose will be considered a missed dose. Administration may resume at the next planned dosing date.

The maximum delay for toxicity before treatment is permanently discontinued will be 3 weeks; however, delays due to other circumstances should be discussed with the Principal Investigator. Delays of >3 weeks must be discussed with the Principal Investigator. Re-treatment will be at the discretion of the Principal Investigator.

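### The only agent-by-agent causality rule in section 7 lists bortezomib, which is not given, and omits carfilzomib and isatuximab, which are.

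*Combined protocol and SAP*

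**What the plan says.** The last part of Attribution (Causality) in section 7.1 reads: "Causality will be assessed for each investigational treatment used in the trial (bortezomib, lenalidomide and dexamethasone". The next sentence sends unexpected and suspected serious reactions to the expedited reporting rules.

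The regimen is stated elsewhere without ambiguity. Section 1.1 describes a study of "once weekly carfilzomib, lenalidomide, dexamethasone, and isatuximab (KRDI) in patients with newly diagnosed, transplant-eligible multiple myeloma". Section 5.1 says: "Carfilzomib, lenalidomide, dexamethasone, and isatuximab will be administered on a 28-day treatment cycle". In maintenance, standard-risk patients receive lenalidomide alone. High-risk patients receive carfilzomib and lenalidomide with isatuximab ("Isatuximab 10 mg/kg IV Day 1 for up to 24 cycles of maintenance (two years), then discontinue"), and dexamethasone as premedication for isatuximab.

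Section 7 has its own list of agents. One adverse event heading names isatuximab as the investigational agent; another names carfilzomib, lenalidomide and dexamethasone as commercial agents. Bortezomib is in neither.

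**The concern.** The sentence is an instruction to investigators, and its list of drugs does not match the trial. Followed literally, it asks for a judgement on a drug that no patient receives under the protocol and asks for none on two drugs that form the core of the regimen. One of those two, isatuximab, is the only drug that section 7 itself calls investigational.

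What is at stake is the record of which drug an event was attributed to. Safety and tolerability of the four-drug regimen is a secondary objective (section 1.1.2). The two omitted drugs are also the two supplied for the trial by their manufacturers: "Sanofi will supply isatuximab free-of-charge, shipped directly to the pharmacy at the study site" (section 5.3.1.10) and "Amgen will supply carfilzomib free-of-charge, shipped directly to the pharmacy at the study site" (section 5.3.2.9). Section 7.4 makes the lead site responsible for reporting serious adverse events to the pharmaceutical partners. If the study forms inherited the list, those reports would draw on records with no causality entry for the partners' own products.

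**Working it through.** No figure in the plan depends on this sentence, so the check is a comparison of text and a count.

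**1. Agents listed against agents given**

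| Agent | Listed in the section 7.1 causality rule | Given (section 5.1) | Section 7 adverse event headings |
|---|---|---|---|
| Bortezomib | yes | no | absent |
| Lenalidomide | yes | yes | commercial |
| Dexamethasone | yes | yes | commercial |
| Carfilzomib | no | yes | commercial |
| Isatuximab | no | yes | investigational |

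Listed but not given: 1 of 3. Given but not listed: 2 of 4. Bortezomib has no dosing, supply or dose-modification text. Apart from this sentence it appears only in the abbreviations, the background and rationale, and the references. Section 5.4 (Prohibited Therapies) bars other anti-myeloma treatment during the study.

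**2. Whether another rule in section 7 supplies the missing requirement**

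The definition of attribution in section 7.1 relates the event to the study treatment as a whole. Section 7.2 requires a causal assessment against the study drug or drugs, for each event, without naming any. The reporting table in section 7.4 has attribution rows but no drugs. None of these asks for causality separately for each drug.

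**3. How far the rest of the protocol uses drug-level attribution**

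- Start of cycle (section 5.2): "Any other lenalidomide, carfilzomib, or isatuximab-related adverse event that may have occurred" must have resolved below Grade 2.
- Isatuximab (section 6.1): 2 rules. The hold applies only if "the event cannot be ascribed to lenalidomide, carfilzomib, dexamethasone, or underlying MM, the isatuximab infusion must be held" to allow recovery. The text after Table 8 adds permanent discontinuation after a prolonged hold for an isatuximab-related event.
- Carfilzomib, Table 9: thrombocytopenia (1); neutropenia and Grade 3 non-blistering rash (2); congestive heart failure, hypertension, heart problems, pericardial effusion, pericarditis and pulmonary hypertension (6); pulmonary toxicities, lung clot, fluid or bleeding, gastrointestinal perforation and other carfilzomib-related toxicity (4). 1 + 2 + 6 + 4 = 13. For heart failure only the dose decrement depends on attribution, not the hold.
- Carfilzomib, Table 10: hepatotoxicity attributable to carfilzomib (1). Total 13 + 1 = 14.

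These counts show how widely the protocol relies on such judgements. They do not estimate how many events would be misrecorded.

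**4. What does not depend on the list**

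The stopping rule and the treatment-related tables in section 12.1 use relatedness to treatment overall. In the section 7.4 table, the unrelated/unlikely row and the possible/probable/definite row agree in five of six columns: all serious events, expected Grade 2 and 3, expected Grade 4, unexpected Grade 4, and Grade 5. Only unexpected Grade 2 and 3 events differ (not required against 5 calendar days), and that distinction also uses overall attribution.

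**The case against.** The strongest reply is that this is a leftover from another protocol with little effect. The governing words cover each investigational treatment used in the trial; bortezomib is not used and isatuximab is, so a site holding the regimen would see that the parenthesis is wrong. Section 7.2 still requires a causal assessment for the study drugs, and section 6 makes investigators separate the agents in practice with the right names. Section 7.4 has serious and reportable events submitted on FDA Form 3500A or a local IRB form, neither described as built for this study. No passage makes reporting to the manufacturers depend on drug-level causality, and section 12.1 plans no tables by individual drug.

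Most of this is correct and limits the consequence. The dose rules in section 6 stand, overall relatedness is still collected, and no planned analysis changes. Three things remain. The general duty in section 7.2 does not ask for a separate entry per drug; the faulty sentence is the only one that does. Reading around the parenthesis is less secure for carfilzomib, which section 7 labels commercial, not investigational. And section 7.2 places serious events on study-specific case report forms as well, so the question of whether those forms copied the list stays open.

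**Conclusion.** The concern holds. The causality rule names one drug that is not given and omits two of the four that are, in contradiction to sections 1.1 and 5.1 and to section 7's own headings. That is certain from the text.

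The consequence is narrower. It is a risk that drug-level attribution for carfilzomib and isatuximab goes unrecorded, and it rests on the assumption that the study's adverse event forms follow this list. The forms cannot be seen, so the assumption is untested. No effect is claimed on the primary endpoint, the stopping rule, the planned safety tables, the reporting timelines or the dose-modification rules. Because the error sits in an operative safety instruction and is cheap to remove, it should be corrected.

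**What to change.** Replace the sentence in section 7.1 with: *Causality will be assessed for each study drug (carfilzomib, isatuximab, lenalidomide and dexamethasone).* Saying study drug also removes the clash with the section 7 heading that calls three of the four commercial.

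Then check that the adverse event and serious adverse event forms have a causality field for each of these four drugs and none for bortezomib. The cost is a one-line protocol correction and the form check. No dose, schedule or clinical rule is touched.
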